Data Management and Quality Assurance: All study data will be entered directly into the electronic data capture (EDC) system. Participating sites will only have access to those data entered by their own institution. All sites will be fully trained on using the on line data capture system, including electronic case report form (eCRF) completion guidelines and help files. The eCRFs will include programmable edits to deliver immediate feedback if data are missing, out of range, illogical or potentially erroneous. A study monitoring plan, including for-cause monitoring, that is appropriate for the study design will be developed and implemented. Site monitoring will be performed by clinical research associates (CRAs) to examine compliance with the protocol and adherence to the data collection procedures, to assess the accuracy and completeness of submitted clinical data, and to verify that records and documents are being properly maintained for the duration of the study. Audits may be conducted at any time during or after the study to ensure the validity and integrity of the study data.

Safety: All SAEs and both serious and non-serious AESI will be recorded in the eCRF, from the patient's first dose of brentuximab vedotin (which may be prior to enrolment) through 30 days after the patient's last dose of brentuximab vedotin. After that time point, only SAEs and both serious and non-serious AESI considered related to brentuximab vedotin will be recorded in the eCRF.

Confidential. Page 7 of 44

Statistical Considerations:

Sample size

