4. STUDY DESIGN

4.1 Study Description

This is a multi-center international prospective, observational cohort study of patients who have been diagnosed with relapsed or refractory CD30+ HL or relapsed or refractory sALCL and are treated with brentuximab vedotin as part of routine clinical care. The study will target the enrolment of approximately 500 patients (at least 50 of whom have a diagnosis of sALCL), who are initiating or are currently being treated with brentuximab vedotin at approximately 75-100 sites in 12-15 countries in Europe and potentially in other countries outside of Europe. Patients already being treated with brentuximab vedotin at the time of enrolment will be considered to be retrospectively enrolled for purposes of analysis and inclusion in the PASS. The sample size for this study was based on the need for more information regarding the occurrence of both serious and non-serious AESI, relative to the

Confidential. Page 15 of 44

size of the current safety database. The study will continue for five years from the date of first patient enrolled. The study will be managed by the contract research organization (CRO) Quintiles, with oversight by Millennium Pharmaceuticals, Inc. (Millennium) project team.

Sites that treat patients with relapsed or refractory CD30+ lymphomas including HL and sALCL will be invited to participate in the study. Country and site selection will depend on the timing of commercial availability of brentuximab vedotin, reimbursement status, and physician product adoption rates in the selected countries to ensure that an adequate number of patients treated with brentuximab vedotin are available for enrolment into the study. The duration of the enrolment period may be extended (or contracted) based on actual patient accrual rates.

Eligible patients will be identified from sites where patients are initiating or already receiving therapy with brentuximab vedotin. No study specific visits or procedures will be required as part of patient participation in the study. Patients will be evaluated according to the physician's standard practice and discretion.

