5.2.2 Planned analyses

5.2.2.1 Primary analyses

Serious Adverse Events (SAEs) and Adverse Events of Special Interest (AESI)

SAEs and AESI (including both serious and non-serious AESI) will be summarized by MedDRA system organ class (SOC) and preferred term (PT). Frequency and incidence proportion for all SAEs and AESI (as defined in Section 4.4.1) will be reported for patients who received at least one dose of brentuximab vedotin while on study.

The incidence rate and the associated 95% CI will be reported for SAEs and AESI.

Time at risk of SAEs and AESI will correspond to current/recent treatment with brentuximab vedotin. Current/recent treatment will be defined as time between the dates of first and last dose plus 30 days. All other follow-up time accrued for the patient will be considered occurring during past treatment with brentuximab vedotin; events reported during the past treatment period will be presented separately.

In addition, select events will be displayed by timing in relation to treatment start (e.g., by number of completed cycles) or time-to-event analysis may be carried out using Kaplan-Meier plots for the occurrence of the first reported occurrence of the adverse event, as appropriate for the event.

Identification and Description of Risk Factors for Peripheral Neuropathy

In addition, multivariable adjusted analysis will be performed to identify and describe risk factors for peripheral neuropathy (e.g., BMI, previous history of neuropathy, known toxic exposures) in the cohort. Risk factors for the first occurrence of new onset or worsening of peripheral neuropathy will be explored using a multivariable adjusted Cox regression model. Model assumptions concerning proportionality will be evaluated graphically in the usual manner. The inclusion of specific risk factors will be described in the SAP. A preliminary univariate analysis of the association of variables of interest with the outcome measure will be

Confidential. Page 24 of 44

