7. SAFETY REPORTING

7.1 Definitions

Adverse events (AEs)

An AE is any untoward medical occurrence in a patient or subject administered a pharmaceutical product and which does not necessarily have to have a causal relationship with the product. An AE can therefore be any unfavorable and unintended sign (including an abnormal laboratory finding, for example), symptom, or disease temporally associated with the use of a product, whether or not considered related to the product. Pre-existing conditions that worsen during a study are considered AEs.

If, according to the investigator, there is a worsening of a medical condition that was present prior to the administration of brentuximab vedotin, this should also be considered a new AE and collected in the eCRF if it meets the definitions of an SAE or AESI described below. Any medical condition present prior to the administration of brentuximab vedotin that remains unchanged or improved is not an AE.

An abnormal laboratory value should not be assessed as an AE unless that value leads to discontinuation or delay in treatment, dose modification, therapeutic intervention, or is considered by the investigator to be a clinically significant change from baseline. When possible, signs and symptoms indicating a common underlying pathology should be noted as one comprehensive event. In cases of surgical or diagnostic procedures, the condition/illness leading to such a procedure is considered as the AE rather than the procedure itself.

Serious adverse events (SAEs)

Serious AE (SAE) means any untoward medical occurrence that at any dose:

• Results in **death**.

Confidential. Page 29 of 44

- Is **life-threatening** (refers to an AE in which the patient was at risk of death at the time of the event. It does not refer to an event which hypothetically might have caused death if it were more severe).
- Requires inpatient hospitalisation or prolongation of an existing hospitalisation (planned hospital admissions or surgical procedures for an illness or disease that existed before the patient was enrolled in the study are not to be considered AEs unless the condition deteriorated in an unexpected manner during the study)
- Results in **persistent or significant disability or incapacity**. (Disability is defined as a substantial disruption of a person's ability to conduct normal life functions).
- Is a congenital anomaly/birth defect.

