7.2.1 Events to be recorded in the eCRF

All SAEs and both serious and non-serious AESI will be recorded in the eCRF, from the patient's first dose of brentuximab vedotin through 30 days after the patient's last dose of brentuximab vedotin. For retrospectively enrolled patients, this includes any SAEs or both serious and non-serious AESI identified in the medical record which occurred prior to study enrolment but after initiating the current regimen of brentuximab vedotin. From 31 days after the patient's last dose of brentuximab vedotin, only SAEs and both serious and non-serious AESI considered related to brentuximab vedotin will be recorded in the eCRF (see Table 3).

Documentation regarding an SAE or both serious and non-serious AESI, observed by the investigator or reported by the patient upon indirect questioning, should be made as to the

Confidential. Page 31 of 44

nature, date of onset, end date, severity, relationship to brentuximab vedotin, action(s) taken, and outcome.

If any of the same SAE or both serious and non-serious AESI, occur on several occasions in the same patient, then the event in question must be documented and assessed each time.

7.2.2 Events to be reported to Millennium Pharmacovigilance & Risk Management (PV&RM) or designee (in addition to being recorded in the eCRF)

All SAEs (regardless of relationship to brentuximab vedotin) and both serious and non-serious AESI considered related to brentuximab vedotin, occurring from the patient's first dose of brentuximab vedotin in the current regimen through 30 days after the patient's last dose of brentuximab vedotin, must also be reported to Millennium PV&RM or designee by faxing a completed SAE Form within one business day after becoming aware of the event (see Table 3). For retrospectively enrolled patients, this includes any SAEs (regardless of relationship to brentuximab vedotin) or AESI, both serious and non-serious, considered related to brentuximab vedotin identified in the medical record which occurred prior to study enrolment but after initiating the current regimen of brentuximab vedotin.

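### The planned-admission exclusion in 7.1 is anchored on enrolment while other event rules run from first dose, so a narrow class of on-treatment SAEs can be lost in retrospective patients only

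*Protocol*

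**What the plan says.** The hospitalisation criterion in the SAE definition (Protocol 7.1) carries a parenthesis. Planned admissions or operations "for an illness or disease that existed before the patient was enrolled in the study are not to be considered AEs". One exception is attached, so that the exclusion holds "unless the condition deteriorated in an unexpected manner during the study".

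The general AE definition, earlier in the same section, judges what is pre-existing by exposure to the drug: "Any medical condition present prior to the administration of brentuximab vedotin that remains unchanged or improved is not an AE".

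The recording rules also start from exposure. The Safety paragraph of the synopsis has SAEs and AESI recorded "from the patient's first dose of brentuximab vedotin (which may be prior to enrolment) through 30 days after the patient's last dose". For retrospective patients, 7.2.1 adds SAEs and AESI "identified in the medical record which occurred prior to study enrolment but after initiating the current regimen of brentuximab vedotin". For the incidence rates, 5.2.2.1 states: "Current/recent treatment will be defined as time between the dates of first and last dose plus 30 days".

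Section 4.1 defines the group concerned: "Patients already being treated with brentuximab vedotin at the time of enrolment will be considered to be retrospectively enrolled". Section 5.1 expects 15 to 20% of the 500 patients, or 75 to 100, to be of this kind.

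**The concern.** A prospective patient enrols before first dose, so nothing that arises on treatment can pre-date enrolment. A retrospective patient has a stretch of treated time before enrolment. The protocol counts that stretch as time at risk and asks for its events, yet the planned-admission exclusion treats a condition that began in it as pre-existing.

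The occurrence of SAEs is the first study objective. Section 5.2.1 presents the two cohorts separately because the volume and nature of reported events may differ between them. A definition that itself removes events from only one cohort adds an artificial difference to that comparison. The planned tabulation of missing items by cohort would not show it, because an event defined as not being an AE is not a missing item.

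**Working it through.** **Size of the affected group.** From 5.1: 0.15 × 500 = 75 and 0.20 × 500 = 100. This reproduces the protocol's figure.

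**Reference points side by side.**

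| Rule | Where | Reference point |
|---|---|---|
| Planned-admission exclusion | 7.1, SAE definition | Enrolment |
| Exception to it | 7.1, SAE definition | During the study |
| What counts as pre-existing | 7.1, AE definition | Administration of the drug |
| Recording window | Synopsis; 7.2.1; Table 3 | First dose; for retrospective patients, start of the current regimen |
| Time at risk | 5.2.2.1 | First dose |

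No section resets the first row for retrospective patients.

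**The same history in two patients.** Each patient starts treatment, then develops a new non-AESI condition, then has a planned admission for it without unexpected deterioration.

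- Prospective patient: enrolment came before first dose, so the condition arose after enrolment. The exclusion does not apply, the hospitalisation criterion is met, and the event is an SAE.
- Retrospective patient, enrolled after the condition began: the condition existed at enrolment, so the admission is excluded. This holds whether the admission falls before or after enrolment.

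The exception does not reliably help the second patient. It requires unexpected deterioration, and its reference to the study can be read as time after enrolment.

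**What is actually lost.** Table 3 collects SAEs and AESI only.

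- The record disappears if the condition is not an AESI, began between first dose and enrolment, led to a planned admission, did not deteriorate unexpectedly, and met no other seriousness criterion.
- If the condition is an AESI it is still recorded, because 7.1 defines AESI regardless of seriousness. It may lose its serious classification.
- The patient drops out of the SAE proportion only if there is also no other SAE.
- In the incidence rate, the event leaves the numerator while the patient's person-time stays in the denominator.

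The exclusion can only remove events, so the error runs one way.

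**Size per patient lost.** Overall, 1/500 = 0.2 percentage points. In the retrospective cohort, 1/100 = 1.0 to 1/75 = 1.3 points.

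**Illustration only.** The documents give no frequency. Assume that 1% to 10% of retrospective patients lose their only SAE in this way.

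- Patients lost: 75 × 0.01 = 0.75 up to 100 × 0.10 = 10.
- Retrospective cohort: 1 to 10 points.
- Overall: 0.75/500 = 0.15 up to 10/500 = 2.0 points.

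The top of this range needs the highest assumed rate, the larger cohort and no other SAE in any of those patients. Given the stacked conditions above, nothing in the protocol supports it.

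**The case against.** The strongest reply is that the section largely protects itself.

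- Section 7.1 treats the condition behind a procedure, not the procedure, as the AE. Excluding the admission therefore does not erase a treatment-emergent condition, which remains an AE under the exposure-based definition.
- AESI are recorded whether serious or not. The sample size in 5.1 rests on AESI precision, so it is untouched.
- Events that are life-threatening, disabling or medically important remain SAEs, and unexpected deterioration restores the event.

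Most of this stands, and it narrows the point to the conditions listed in the working. It does not remove the point. A non-AESI condition that remains an AE but is no longer serious is not collected, so for that class the safeguard leaves nothing in the database.

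A reader might infer that admissions for on-treatment conditions are dropped generally in retrospective patients. The text does not support that: the exclusion covers planned admissions and procedures only, and unplanned ones count in both cohorts.

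A reader might also infer that 7.1 and 7.2.1 give opposite recording orders for every treatment-emergent event. They do not. Section 7.2.1 asks for SAEs and AESI, and 7.1 decides what an SAE is. The conflict lies between the reference points within 7.1, and between the exclusion and the recording and risk windows. For the same reason 7.2.1 does not cure the problem: a site that applies 7.1 first would not identify the event as an SAE.

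**Conclusion.** The exclusion is wrong as written for retrospectively enrolled patients. Taken literally, it can remove a treatment-emergent SAE, or the serious classification of an AESI, in that cohort and not in the other. This conclusion rests on the wording alone and on retrospective patients being on treatment before enrolment, not on any assumed frequency.

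The bias is an under-count of SAEs, confined to an expected 75 to 100 of 500 patients. It cannot be quantified from the documents and is probably small. A reader might infer from the illustrative range that the overall SAE proportion is materially biased. The documents do not support that, because they give no rate of such admissions and the calculation assumes that each lost event is the patient's only SAE. The correction is worth making because SAE occurrence is a main objective, the affected cohort is reported separately, and the change to the text is short.

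**What to change.** In the hospitalisation criterion of 7.1, tie the exclusion to illness present before the first dose of brentuximab vedotin in the current regimen, and tie its exception to unexpected deterioration after that dose. Align the neighbouring sentences in 7.1 on pre-existing and worsening conditions to the same reference point. They now refer variously to a study and to administration of the drug, which could differ for a re-treated patient. Add a line to the eCRF completion guideline telling sites to apply this rule to retrospective charts.

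No visit, test or treatment changes. The cost is a written amendment under 6.6, with ethics committee submission where it is classed as substantial (8.4). Retrospective charts already abstracted must also be re-checked; the first patient enrolled in June 2013 and the current amendment is dated March 2014, so some may already exist.

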7.2 Procedures for Recording and Reporting SAEs and AESI

Table 3 Serious and Non-Serious Adverse Event Recording and Reporting

Tuble e belloub ullu 1 (oll bell	Table 5 Serious and Non-Serious Muverse Event Recording and Reporting						
Time Point	Data Collected	Data Reported to Millennium PV&RM or designee					
From first dose of brentuximab vedotin through 30 days after last dose of brentuximab vedotin	SAEsAESI	 SAEs AESI considered related to brentuximab vedotin 					
From 31 days after last dose of brentuximab vedotin through the end of patient's participation in the study	 SAEs considered related to brentuximab vedotin AESI considered related to brentuximab vedotin 	 SAEs considered related to brentuximab vedotin AESI considered related to brentuximab vedotin 					

7.2.1 Events to be recorded in the eCRF

All SAEs and both serious and non-serious AESI will be recorded in the eCRF, from the patient's first dose of brentuximab vedotin through 30 days after the patient's last dose of brentuximab vedotin. For retrospectively enrolled patients, this includes any SAEs or both serious and non-serious AESI identified in the medical record which occurred prior to study enrolment but after initiating the current regimen of brentuximab vedotin. From 31 days after the patient's last dose of brentuximab vedotin, only SAEs and both serious and non-serious AESI considered related to brentuximab vedotin will be recorded in the eCRF (see Table 3).

Documentation regarding an SAE or both serious and non-serious AESI, observed by the investigator or reported by the patient upon indirect questioning, should be made as to the

Confidential. Page 31 of 44

nature, date of onset, end date, severity, relationship to brentuximab vedotin, action(s) taken, and outcome.

If any of the same SAE or both serious and non-serious AESI, occur on several occasions in the same patient, then the event in question must be documented and assessed each time.

7.2.2 Events to be reported to Millennium Pharmacovigilance & Risk Management (PV&RM) or designee (in addition to being recorded in the eCRF)

All SAEs (regardless of relationship to brentuximab vedotin) and both serious and non-serious AESI considered related to brentuximab vedotin, occurring from the patient's first dose of brentuximab vedotin in the current regimen through 30 days after the patient's last dose of brentuximab vedotin, must also be reported to Millennium PV&RM or designee by faxing a completed SAE Form within one business day after becoming aware of the event (see Table 3). For retrospectively enrolled patients, this includes any SAEs (regardless of relationship to brentuximab vedotin) or AESI, both serious and non-serious, considered related to brentuximab vedotin identified in the medical record which occurred prior to study enrolment but after initiating the current regimen of brentuximab vedotin.

From 31 days after the administration of the patient's last dose of brentuximab vedotin and through the end of the patient's participation in the study, only SAEs considered related to brentuximab vedotin and AESI, both serious and non-serious, considered related to brentuximab vedotin should be reported to Millennium PV&RM or designee by faxing a completed SAE Form within one business day after becoming aware of the event.

The SAE Form, created specifically by Millennium, will be provided to each study site. SAEs reported to Millennium PV&RM or designee will be followed to resolution per standard SAE follow-up processes. Follow-up information on reported events may be requested by Millennium or designee. Information faxed to Millennium on a SAE Form must be consistent with the data recorded in the eCRF.

All completed SAE Forms should be faxed to:

For country-specific SAE Reporting Contact Information, please refer to Appendix 3

SAEs and both serious and non-serious AESI considered related to brentuximab vedotin a will be reported to local and regional health authorities by the sponsor, when appropriate, in accordance with applicable local and regional regulations. Compliance with any applicable site-specific requirements related to the reporting of SAEs or other safety information to the local IEC that approved the study will be maintained.

Confidential. Page 32 of 44

7.3 Procedures for Reporting Pregnancies

If a patient exposed to brentuximab vedotin becomes pregnant or suspects that she is pregnant while participating in this study, the investigator should be informed immediately. The sponsor must also be contacted immediately by faxing a completed Pregnancy Form to Millennium PV & RM or designee (for country-specific contact details, refer to Appendix 3). The pregnancy must be followed for the final pregnancy outcome.

If a female partner of a male patient exposed to brentuximab vedotin becomes pregnant during the male patient's participation in this study, the sponsor must also be contacted immediately by faxing a completed Pregnancy Form to Millennium PV & RM or designee (for country-specific contact details, refer to Appendix 3). Every effort should be made to follow the pregnancy for the final pregnancy outcome.

